10.1.3 Combining the multiple imputation results to derive TEAR status

At this point there should be two sets of imputed data, each containing 30 records per subject, with all visits on the same record. These will need to be merged by subject and imputation. Then the TEAR values will be computed for each subject and analyzed. There are 3 steps:

1. Merge the imputed ADA binary response dataset with the imputed ADA titer dataset, by `usubjid avisitn _imputation_`. Then generate TEAR responder status based on the Week 24 (Visit 15) ADA values using the same algorithm as was used for the original data. This dataset will have one record per imputation per subject, but the TEAR values will be non-missing for all subject visits. Note that the variable TEAR may vary from imputation to imputation for the same subject. That is supposed to happen.
2. Run the primary efficacy analysis to create the 90% confidence interval using the Wald confidence limit method within each imputation. That will result in 30 confidence intervals, one for each imputation.
3. Combine the 30 confidence intervals to generate one summary confidence interval to be presented in the table.

Step 1.

Merge the imputed titer values by `usubjid avisitn _imputation_` to make a single dataset. Then create a new variable for TEAR status by following the ADaM specs for the definition of TEAR events, but using the new imputed ADA data. Again, the dataset will contain one record per imputation per subject, with a new response variable added to every record. For the purposes of the next steps below, this new response variable will be called TEAR.

- a. If the subject was ADA negative at baseline then do:
 - i. If any of RESP8–RESP15 is positive, then TEAR=1 for that imputation for that subject
 - ii. Else TEAR=0 for that imputation for that subject
- b. Else if subject was ADA positive at baseline then do:
 - i. If $ADA_x / ADA_0 \geq 4$ for any visit, where x is in 8–15, then TEAR = 1;
 - ii. else TEAR=0

Step 2.

Use code similar to what was used to analyze the primary efficacy endpoint, but run the code by `_imputation_`. For example,

```
/** step 2: Analyze the imputed datasets */  
proc freq data=imputed;  
by _imputation_;  
table trt*tear / alpha=0.10 riskdiff (cl= wald column=2)  
;  
output=outmi riskdiff;  
run;
```

Step 3.

Combine the 30 estimated statistics into one using PROC MIANALYZE.

```
proc mianalyze data=outmi;  
modeleffects _rdif1_ ;  
stderr e_rdif1;  
ods output parameterestimates=parms;  
run;  
  
proc print data=parms;  
var estimate stderr lclmean uclmean probt;
```

```
run;
```

10.1.4 Multiple imputation for HbA1c.

HbA1c is measured at baseline and at Weeks 12 and 24 (visits 11 and 15). For purposes of these specifications, let HB_x represent the continuous value for HbA1c value at Visit x, where x takes the values 0 (for Baseline) or 11 or 15. The seed that will be used in the multiple imputation of ADA titer will be 24637883. The imputations will be combined using a mixed model for repeated measures.

There are 6 steps to this process:

1. Create a dataset with one record per subject, containing all values of HbA1c for all weeks (Baseline and Weeks 12 and 24 on one record); that is, each record would contain variables for HB₀, HB₁₁, and HB₁₅.
2. Run 30 Markov Chain Monte Carlo (MCMC) imputations to make the missing values in the dataset have a monotone missingness pattern. This will produce a dataset with an index variable `_imputation_` and otherwise the same variables as the input dataset. It will have one record per imputation per subject.
3. Run a pattern mixture model regression imputation on each imputed dataset from Step 2. This will generate a dataset with the same structure as the input dataset, but will have the missing values filled in.
4. Transform the dataset back into one record per subject per visit, with imputation number retained on each record.
5. Run a mixed model for repeated measures on the imputed datasets.
6. Combine the imputations to provide summary statistics.

Step 1.

The dataset for this imputation has to put the values for all weeks onto one record. That is, the dataset would have one record per subject, with 3 values for HB₀, HB₁₁, and HB₁₅.

One way this can be accomplished is the following:

```
data analysis (keep=usubjid trtp HB0 HB11 HB15);  
set indata;  
by usubjid avisitn;  
array y {3} HB0 HB11 HB15;  
retain HB0 HB11 HB15;  
if first.usubjid then do;  
    hb0 = base;  
    hb11 = .;  
    hb15 = .;  
end;
```

```
if avisit = 11 then hb11 = aval;  
if avisit = 15 then hb15 = aval;  
if last.usubjid then output;  
run;
```

Step 2.

```
/** step 2: Create monotone missingness using MCMC  
imputation */  
proc mi data=analysis seed=24637883 nimpute=1  
out=outdata1;  
mcmc impute=monotone;  
var hb0 hb11 hb15;  
run;
```

Step 3.

```
/** step 3: Perform PMM regression imputation */  
proc sort data=outdata1;  
run;  
  
proc mi data=outdata1 seed=24637883 nimpute=30  
out=outdata2;  
by treatment;  
monotone reg(hb11 hb15 / details);  
mnar model (hb11 hb15 / modelobs=ccmv(k=1));  
var hb0 hb11 hb15;  
run;
```

Step 4.

Reverse the process from Step 1, creating one record per subject visit, retaining the imputation number on each record.

Step 5.

Use code similar to what was used to analyze the primary efficacy endpoint, but run the code by `_imputation_`. For example,

```
/** step 5: Analyze the imputed datasets */  
proc sort data=imputed;  
by _imputation_ subjid avisitn;  
run;  
  
proc mixed data=imputed;  
by _imputation_;
```

```
class trt avisitn dosetime site;
model chg = trt avisitn dosetime site trt*avisitn base /
ddfm=kr s;
repeated avisitn / type=un;
lsmeans trt*avisitn / diff cl;
ods output ConvergenceStatus=converge;
ods output diffs=trtdiff;
run;
```

Convergence status is assessed by the condition that:

```
if pdg=1 and pdh=1 and status=0
```

in the dataset converge above, then model has converged. In the above code, if the model does not converge, replace the type=un option by each of the following: type=toeph, type=toep, and type=cs. You will also need to replace ddfm=kr with ddfm=bw. Choose the best fit model by checking the AIC and selecting the model with the lowest one. Please contact the statistician if this step is necessary.

Step 6.

Combine the 30 estimated statistics into one using PROC MIANALYZE.

```
data trtdiff;
set trtdiff (where=(avisitn=_avisitn));
run;

proc sort data=trtdiff;
by avisitn _imputation_;
run;

[figure not shown]
proc mianalyze data=trtdiff;
by avisitn;
modeleffects estimate ;
stderr stderr;
ods output parameterestimates=parms;
run;

proc print data=parms;
var avisitn estimate stderr lclmean uclmean probt;
run;
```

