If baseline value is missing, the missing baseline value will be imputed with multiple imputations (6 imputations) using no missing baseline values from same treatment group. After imputation, the TEAR criteria will then be applied to each imputed dataset to obtain if a subject is TEAR positive or negative, and the treatment difference and 90% confidence interval will be estimated using Wald confidence limit method. The result will be combined over all imputations by SAS PROC MIANALYZE.

Tipping-point analysis will be performed via the method proposed by Liublinska and Rubin (2014). This will include a graphic display to indicate the tipping point analysis for the TEAR status binary outcome. A graphic display (heating map) is used to indicate the tipping point analysis results with missing values as TEAR positive. The treatment differences are presented as values in the heat map. The graph will be displayed to show the sensitivity ranging from missing favour testing treatment to missing favour reference treatment.

For tipping-point analysis, the number of subjects with missing data include 1) subjects who are missing all post-baseline ADA data, 2) subjects with partially missing ADA data whose TEAR status cannot be determined as positive or negative, and 3) subjects who are missing ADA data at baseline. If a subject with partially missing ADA data already meets the TEAR criteria, the subject is not considered as a subject with missing data.

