For continuous-valued ADA titer, missing values prior to the last observed visit will be filled in with MCMC imputation to make the dataset monotone. Missing values after discontinuation will be imputed by regression imputation of the monotone missing dataset. If there are at least 6 retrieved dropouts in each treatment arm, then a pattern mixture model estimated from the retrieved values will be used for regression imputation of missing values. Otherwise, the complete case missing values method will be used. Missing values for the binary response variable will be imputed using a logistic regression multiple imputation model. A monotone missingness pattern will be created by taking a random draw from the binomial distribution with the same probability as the observed responses from the same treatment group at the same visit.

Pattern mixture models will be fit separately for ADA binary response and for ADA titer. Binary response will be imputed using a logistic regression imputation model, while ADA titer will use a continuous-valued regression. Independent variables in the regression will include the values at all prior visits. Each imputation will be repeated 30 times with a seed of 40872021 for ADA binary response and a seed of 41671703 for ADA titer. Code for the multiple imputation analyses is presented in Appendix 10.1.

If baseline value is missing, the missing baseline value will be imputed with six imputations based on binomial distribution using probability of no missing baseline values from same treatment group.

After imputation, the dataset containing the imputed visitwise TEAR positive or negative status binary response and the dataset containing the imputed ADA titer values will be merged by subject, visit, and imputation number. The Week 24 values will then be used to assign the status of TEAR positive or negative, as follows:

If the subject was ADA negative at baseline, then this subject will be considered TEAR positive if any post-baseline observed or imputed value was ADA positive; otherwise, the subject will be considered TEAR negative. The imputed titer values will not be considered in subjects who are ADA negative at baseline.

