10.1 Multiple imputation

Multiple imputation will be applied to fill in missing values for ADA binary response and for ADA titer.

For binary ADA response, if baseline ADA value is missing, the missing baseline value will be imputed (6 imputations) based on binomial distribution using probability of no missing baseline values from the same treatment group. After imputations, for subjects with negative baseline ADA (Section 10.1.1) missing post-baseline binary response (positive or negative) will be imputed using logistic regression multiple imputation. For subjects who are ADA positive at baseline (Section 10.1.2), missing post-baseline ADA continuous titer values will be imputed with same treatment group non-missing subjects using continuous MI model.

The steps are summarised below:

Section 10.1.1 describes the methodology for imputation of binary response, while Section 10.1.2 covers the imputation of continuous ADA titer, and Section 10.1.3 puts them together.

10.1.1 Multiple imputation for binary ADA response if baseline ADA is negative.

For purposes of these specifications, let $RESP_x$ represent the binary value (0 or 1) at Visit x , where x takes the values 0 (for Baseline) or 8–15. The seed that will be used in the multiple imputation of ADA binary response will be 40872021.

Missing values will be obtained from logistic regression imputation on the observed values of binary response. A fully conditional specification (FCS) method will be used to impute values from a non-monotone missing data pattern.

There are 3 steps to this process:

1. Create a dataset with one record per subject, containing all values of $RESP$ for all weeks (Baseline and Weeks 2–24 on one record); that is, each record would contain variables for $RESP_0$ and $RESP_8$ – $RESP_{15}$. The subject-level $RETRIEVED$ variable described in Section 8.7.2.1 can also be generated at this time for subjects who discontinued treatment, based on whether values after treatment discontinuation

- were retrieved (set retrieved=1) or remain missing (set retrieved=0).
2. Fill in missing values to make a monotone missing data pattern, by drawing random TEAR values from the binomial distribution based on the TEAR frequencies for the given visit within treatment group.

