 3. Run a pattern mixture model logistic regression to impute missing values to generate 30 imputed datasets. This will generate a single pooled dataset containing one observation per subject per imputation. All missing values will have been filled in for each subject.

Step 1.

The dataset for this imputation has to put the values for all weeks onto one record. That is, the dataset would have one record per subject, with 8 values for RESP0 and RESP8–RESP15. One way this can be accomplished is the following:

```
data analysis (keep=usubjid RESP0 RESP8-RESP14);
set indata;
by usubjid avisitn;
array R {9} RESP0 RESP8-RESP15;
retain RESP0 RESP8-RESP15;
if first.usubjid then do;
    resp0 = base;
    do visit = 8 to 15;
        R{visit} = .;
    end;
end;
do visit = 8 to 15;
    if avisit = visit then R{visit} = aval;
end;
if last.usubjid then output;
run;
```

STEP 2.

First a flag needs to be created to indicate which missing values need to be filled in. This is a visit-level variable for each subject. For explanatory purposes, this variable will be referred to as EMPTY_x for Visit x. For each visit where a subject has a missing value, use the logic below:

- If there is a non-missing value for any visit AFTER Visit x, then EMPTY_x=0;
- Else if there are no non-missing values for any of the remaining visits, then EMPTY_x=1;

Then all records with EMPTY_x=1 have to have their RESP_x value filled in with a randomly generated 0 or 1. One way this can be accomplished is the following:

```
/** step 2: Make missingness monotone */  
%global mylrate novrate;
```

```
%macro getrate(visnum);
```

```
    proc sort data=indata;  
        by trtgroup;  
    run;  
    ods exclude all;  
    proc freq data=indata;  
        by trtgroup;  
        table RESP&visnum;  
    ods output onewayfreqs=pct;  
    run;  
    ods exclude none;
```

```
    data binom;  
        set pct (where=(RESP&visnum=1));  
        probresp = percent/100;  
        if trtgroup="MYL-1601D" then call  
            symput("mylrate",probresp);  
        else if trtgroup="NOVOLOG" then call  
            symput("novrate",probresp);  
    run;
```

```
%mend getrate;
```

```
%macro fillin (visit);
```

```
    %getrate(&visit);
```

```
    data indata;  
        set indata;  
        if empty&visit=1 then do;  
            if trtgroup="MYL-1601D" then  
                RESP&visit=ranbin(86537043,1,&mylrate);  
            else if trtgroup="NOVOLOG" then  

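### SAP 10.1.3 pools 30 imputations, which fits only one draw of a missing baseline ADA, although 7.2.1, 8.7.2.1 and 10.1 require six

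*SAP*

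**What the plan says.** **Baseline stage.** SAP 7.2.1 states that "the missing baseline value will be imputed with multiple imputations (6 imputations) using no missing baseline values from same treatment group". SAP 8.7.2.1 repeats the six and adds that they are binomial draws. Appendix 10.1 says that "the missing baseline value will be imputed (6 imputations) based on binomial distribution" and places this step first: only after it are subjects sent to the baseline-negative branch (10.1.1) or the baseline-positive branch (10.1.2).

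**Post-baseline stage.** SAP 8.7.2.1 says "Each imputation will be repeated 30 times with a seed of 40872021 for ADA binary response", and the same number applies to titer under a second seed. The code in 10.1.1 and 10.1.2 uses `nimpute=30`.

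**Combination.** Section 10.1.3 starts from "two sets of imputed data, each containing 30 records per subject, with all visits on the same record". Its Step 1 instruction is "Merge the imputed titer values by `usubjid avisitn _imputation_` to make a single dataset". It says that each subject has a single record in each imputation, runs the Wald analysis by `_imputation_`, and pools 30 results with PROC MIANALYZE.

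**Background.** Protocol 7.2.2 specifies single imputation of a missing baseline. The SAP revision history records that V3.0 changed this to multiple imputation and added a programming flow chart to Section 10.

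**The concern.** Baseline ADA status decides which TEAR criterion applies: any later positive result for a baseline-negative subject, or a fourfold titer rise for a baseline-positive one. For a subject with no baseline result, TEAR status can therefore change with the draw. V3.0 moved from one draw to several, which lets that uncertainty enter the confidence interval.

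The combination step does not appear to have followed. It has no place for six baseline values per subject, and the printed figures of six, 30 and 30 cannot all hold. A programmer has to choose a reading, and the one that the example code fits restores a single baseline draw. The primary difference, and the margin computed from the NovoLog rate, would then depend on one random number for each affected subject, and the interval would treat that number as known.

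**Working it through.** **Step 1: can the printed 30 be reproduced?**

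- One baseline value followed by `nimpute=30`: 1 × 30 = 30. This matches 10.1.3 but not the six draws.
- Six baseline draws, each followed by `nimpute=30`: 6 × 30 = 180. This matches 7.2.1, 8.7.2.1 and 10.1 but not 10.1.3.
- Six baseline draws, each followed by five imputations: 6 × 5 = 30. This matches the six and 10.1.3 but not `nimpute=30`.

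Only the single baseline draw agrees with both `nimpute=30` and 10.1.3.

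**Step 2: what does the printed code carry?** Step 1 of 10.1.1 and of 10.1.2 builds one record per subject. It sets `RESP0` or `ADA0` at the subject's first record and closes with "if last.usubjid then output". If six stacked copies of a subject went in, one record with one baseline would come out. The later PROC MI calls have no BY variable for a baseline draw, and neither does the merge. In 10.1.2 the MCMC step includes `ada0` in its variable list but runs with `nimpute=1` (its description says 30), so a baseline titer filled there would be shared by all 30 records.

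**Step 3: how much variance does one draw omit?** The inputs from the documents are 250 subjects per arm and z = 1.645 (SAP 5 and 8.7.2.1). The number of missing baselines per arm, k, is not given, so 1, 5 and 10 are assumptions. The TEAR rate p is taken as equal in both arms.

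- Within-imputation variance: W = 2p(1 − p)/250. At p = 0.30, W = 0.42/250 = 0.00168.
- 90% half-width: 1.645 × √0.00168 = 6.74 points.
- Ceiling on the omitted variance: a subject's TEAR status is 0 or 1, so its variance over draws is at most 0.25. With independent draws, B ≤ 2 × k × 0.25/250². For k = 5 this is 2.5/62,500 = 0.00004.
- Ratio for k = 5: B/W = 0.00004/0.00168 = 2.4%.
- Half-width with the omitted part restored: 1.645 × √(W + (1 + 1/30)B) = 1.645 × √0.0017213 = 6.82 points.

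Each cell below gives the maximum B/W and then the corrected half-width in points.

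| TEAR rate | Half-width with one draw | k = 1 | k = 5 | k = 10 |
|---|---|---|---|---|
| 10% | 4.41 | 1.1%; 4.44 | 5.6%; 4.54 | 11.1%; 4.66 |
| 30% | 6.74 | 0.5%; 6.76 | 2.4%; 6.82 | 4.8%; 6.91 |
| 50% | 7.36 | 0.4%; 7.37 | 2.0%; 7.43 | 4.0%; 7.51 |

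For scale, the margin at 30% is 12.0 points in SAP Table 2. It is reproduced by (1.645 + 1.282) × √0.00168 = 11.99 points, using the 0.95 and 0.90 normal quantiles in the code of 10.2.

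**The case against.** **The link may be in the flow chart.** The Section 10 chart was added in the same SAP version as the six imputations, and we cannot see it. This stands as a limit: we cannot say that the link is absent from the plan. But the chart cannot make the printed numbers agree. A nested 6 × 30 would contradict the 30 records and 30 intervals in 10.1.3, and a 6 × 5 scheme would contradict `nimpute=30`.

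**The code is only an example.** Step 1 is offered as one possible way, and as printed it would not run: a nine-element array is indexed from 8 to 15, and the binary keep list drops `RESP15`. This also stands, so the production program may differ. The mismatch does not rest on the code alone, because the prose of 8.7.2.1 and 10.1.3 gives the same figures.

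**Few subjects may be affected.** SAP 7.1 takes the last non-missing value before the first dose, and immunogenicity is also sampled at screening. On that rule both samples must be missing. Protocol 6.5.2.4 names the Visit 6 sample as baseline, which could leave more subjects without one. The point about size stands.

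**A stronger reading.** A reader might infer that affected subjects, or the whole data set, enter the analysis six times, with a falsely narrow interval and an inflated error rate. The documents do not support this. Section 10.1.3 says that each subject has a single record in each imputation, which rules out replicated copies. Nor are a single draw and six-fold counting the only possibilities: 180 uniquely indexed data sets, or six draws spread over 30 imputations, could also be analysed. The nesting behind 180 is itself inferred from the order of steps in 10.1; the SAP does not state it.

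**Conclusion.** The inconsistency is real and lies in the primary analysis. Six baseline draws, 30 post-baseline imputations and 30 pooled results cannot all be carried out as printed, and the visible code fits one baseline draw, as under single imputation.

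Taken literally, the interval leaves out the uncertainty in the baseline draw. At a 30% rate and up to 10 missing baselines per arm, it would be too narrow by at most 6.91 − 6.74 = 0.17 points on each side, against a 12.0-point margin. At a 10% rate the ceiling is 4.66 − 4.41 = 0.25 points, against 7.9 points in Table 2. These figures rest on assumed counts of missing baselines and on a worst-case 50:50 chance of TEAR over the draws, so the real effect is probably smaller. It would be unlikely to change the equivalence conclusion unless the result were close to the margin.

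The reason to act is that the primary analysis should be reproducible from the plan, and that the change to multiple imputation should take effect.

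**What to change.** Replace the six baseline imputations by one baseline draw inside each of the 30 imputations:

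- Index the draw by `_imputation_`, 1 to 30, and send the subject to the baseline-negative or baseline-positive branch according to that draw.
- Run Steps 1 to 3 of 10.1.1 and 10.1.2 BY `_imputation_` with `nimpute=1`. In 10.1.2 this includes the MCMC step, so that a subject drawn positive receives a baseline titer from the same imputation.
- Merge in 10.1.3 on subject and the same `_imputation_`.

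Each subject then has one completed record per imputation, and 30 results are pooled.

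The alternative is to keep six draws, give every baseline draw and post-baseline imputation a unique joint index, change 30 to 180 throughout 10.1.3, and pool all 180. The first option is simpler. It also avoids groups of data sets that share a baseline draw, which the usual pooling rule treats as independent.

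Either way, align 7.2.1, 8.7.2.1, 10.1 to 10.1.3 and the flow chart. Two other details in 10.1.3 need correction at the same time: the wide records carry no `avisitn` to merge on, and the PROC MIANALYZE step prints limits without `alpha=0.1`, whereas 8.7.2.1 computes the 90% limits from 1.645 standard errors.

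The cost is SAP wording and a few lines of code. No new data are needed, and the extra computing is negligible.
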